9.4.4 Safety Analysis

All safety analyses will be conducted on the Safety Analysis Set.

Treatment-emergent adverse events (TEAEs) defined as all events beginning or worsening from Cycle 1, Day 1 through 30 days following study treatment completion, will be coded according to the most current version of the Medical Dictionary for Regulatory Activities (MedDRA) and will

CONFIDENTIAL

Protocol KB-ENTO-3001 v4.0

(Amendment 3.0)

be summarized by treatment group, system organ class, and preferred term. Unless otherwise specified, only TEAEs will be reported in safety summaries and listings.

Additional summaries by seriousness, severity, causality, and outcomes will also be prepared. Adverse events leading to ENTO dose reduction or discontinuation as well as those with an outcome of death will be summarized with descriptive statistics. Changes from baseline in selected laboratory assessments of interest will be summarized by treatment group and severity grade.

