All subjects who achieve morphologic CR, CRh, or CRi upon completion of Chemotherapy Cycle 2 may initiate or continue consolidation therapy in combination with ENTO or placebo (in accordance with their original randomized treatment assignment), as outlined in [Table 5](#) at the investigator's discretion either instead of or as a bridge to hematopoietic stem cell transplant.

Table 5: Treatment Phase –Consolidation

	Age < 60 years	Age \geq 60 years
Cytarabine	3.0 g/m ² , BID over 3 hours on Days 1, 3 and 5 every 28-35 days for up to 3 cycles*	1.5 g/m ² , BID over 3 hours on Days 1, 3 and 5 every 28-35 days for up to 3 cycles*

For subjects with < 5% residual blasts post-Induction Cycle 1, Consolidation Cycle 1 will consist of Chemotherapy Cycle 2. For patients with \geq 5% residual blasts post-Induction Cycle 1, Induction Cycle 2 ([Table 4](#)) will consist of Chemotherapy Cycle 2 with consolidation beginning thereafter. All subjects are eligible to receive up to 3 cycles of high dose cytarabine after Chemotherapy Cycle 2.

All subjects will undergo an End-of-Study Treatment Visit 30 ± 7 days after the last study treatment (either ENTO/placebo or chemotherapy, whichever is later) or prior to initiation of follow-on therapy (eg, maintenance therapy, HSCT), if sooner than 30 ± 7 days after last study treatment.

All subjects regardless of their post-remission status will be followed monthly for 3 months after the End-of-Study Treatment Visit and thereafter at least once every 3 months for progression/relapse, first salvage therapy, and survival until study termination. Unscheduled study visits at other time points are permitted in the setting of suspected leukemic recurrence or for evaluation and management of post-treatment sequelae.

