7.0 Discontinuation of Study Treatment/Participation

7.1 Discontinuation of Study Treatment

Subjects may discontinue study medication at any time at his/her own request or may be discontinued at the discretion of the investigator for safety, behavioral, or compliance reasons.

Subjects must discontinue study medication for the following reasons:

- Recurrence of leukemia after a response
- Failure to achieve (or maintain) CR, CRh or CRI post-Chemotherapy Cycle 2
- Death
- Withdrawal of consent
- An AE or intercurrent illness that precludes further administration of protocol therapy or participation in the study
- Need for, or use of a prohibited concomitant medication
- Hematopoietic stem cell transplantation
- Pregnancy

If study treatment is permanently discontinued for any reasons, subjects shall remain in the study for long-term follow-up. See [Table 7](#) for assessments required for the End-of-Treatment evaluation and long-term follow-up.

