9.2 Sample Size Determination

Based on a completed study of newly diagnosed AML subjects treated with ENTO, it is anticipated that 87% of *NPM1*-m subjects will achieve CR ([Walker 2020](#)). Based on analysis of a historical dataset from the Cancer and Leukemia Group B Alliance ([Mims et al, 2021](#)) showing a 68% CR rate in 107 *NPM1*-mutated/*FLT3-ITD* negative patients ≥ 60 years of age treated with 7+3 induction, a conservative estimate of 70% CR rate for placebo is assumed for sample size determination. The MRD negative rate among placebo subjects achieving CR is assumed to be 60% ([Ivey et al, 2016](#)). Alternatively, it is hypothesized that 80% of subjects with CR receiving ENTO will be MRD negative. A sample size of 90 subjects per group (total of 180 subjects) will provide $> 97\%$ power to detect a difference in the MRD negative CR rate of 28% (87% x 80% = 70% for ENTO vs 70% x 60% = 42% for placebo) with a 2-sided alpha level of 0.05 (PASS 2008: Two sample test of Proportion Module). Up to 10% over enrollment is allowable in order to account for technical or logistical barriers (eg. inadequate bone marrow aspirate or poor sample quality) related to the ascertainment of MRD status in patients who achieve CR post-Chemotherapy Cycle 2.

Assuming the two-year EFS rate for the control group is 63% (hazard rate of 0.231), a total of 124 events (70 in the placebo arm, 54 in the ENTO arm) would be sufficient to provide 80% power to detect a hazard ratio of 0.6 for EFS (PASS 2008: log rank tests (Lakatos) [Hazard Rate] module) assuming 2-sided alpha = 0.05 and a total study duration of 60 months.

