9.4.1 General Considerations

Summary statistics and listings will be used to analyze the study data. Continuous variables will be summarized by means, standard deviations, medians, interquartile ranges, minimal and maximal values. Categorical variables will be summarized by number and percentage. Any statistical testing will be conducted at the alpha = 0.05 level (2-sided).

Unless otherwise specified, data summaries and analyses described below will be reported by treatment group.

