6.5.1. Adverse Events

Adverse events will be mapped to the MedDRA version in effect at the time of database lock. TEAEs will be summarized by treatment group using system organ class and preferred term.

If a subject experiences multiple events that map to a single preferred term, the event of greatest severity will be assigned to the preferred term for the appropriate summaries. Subjects with events mapping to multiple preferred terms within the same system organ class will be counted once at the system organ class level.

Separate summaries for treatment-emergent serious adverse events (TESAEs), TEAEs by severity, TEAEs related to study medication, TEAEs leading to ENTO/placebo dose reduction, interruption, discontinuation, and TEAEs with an outcome of death will be generated.

Missing onset dates will be imputed as previously outlined in [Section 4.4.4.4](#).

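### Pooled crude TEAE percentages would mix any ENTO effect with the extra consolidation that a higher response rate brings; the artefact is conditional and modest, and one phase-limited table largely addresses it

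*Protocol*

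**What the plan says.** Protocol 9.4.4 defines TEAEs as "all events beginning or worsening from Cycle 1, Day 1 through 30 days following study treatment completion" and says that they will "be summarized by treatment group, system organ class, and preferred term". Protocol 9.4.1 sets the statistic: "Categorical variables will be summarized by number and percentage". SAP 6.5.1 repeats the layout: "TEAEs will be summarized by treatment group using system organ class and preferred term". It counts a subject once per preferred term, at the worst severity. SAP 4.4.4 takes study treatment to include chemotherapy as well as ENTO/placebo, so the window follows whichever ends later.

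Treatment length depends on response. Protocol 7.1 lists among the reasons for stopping study medication "Failure to achieve (or maintain) CR, CRh or CRI post-Chemotherapy Cycle 2" and "Hematopoietic stem cell transplantation". Protocol 4.1 says "All subjects are eligible to receive up to 3 cycles of high dose cytarabine after Chemotherapy Cycle 2". Read alone, that sentence covers everyone, but the paragraph before Table 5 and footnote p of Table 7 offer this consolidation to subjects in CR, CRh or CRi. Footnote p leaves the number of cycles to the investigator.

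Protocol 9.2 builds its primary-endpoint assumption as "87% x 80% = 70% for ENTO vs 70% x 60% = 42% for placebo", where 87% and 70% are the CR rates.

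Neither document plans an adverse event table by treatment phase, an exposure-adjusted rate or a time-to-first-event analysis, and the SAP section 10 output list has none. SAP 6.3 does summarise days on drug, cumulative dose, cycles completed and dose intensity by arm, with the chemotherapy part split into Induction and Consolidation.

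**The concern.** A secondary objective is the safety of ENTO compared with placebo. A subject who responds may receive up to three further cytarabine cycles with study medication and is observed for adverse events throughout. A non-responder leaves the window much earlier. If more ENTO subjects respond, the ENTO arm gets more chemotherapy and more days in which an event can count.

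Protocol 2.4 itself attributes most TEAEs in the earlier ENTO study to what intensive induction and consolidation, and the leukaemia, would be expected to cause. Extra consolidation therefore adds events whether or not ENTO is toxic. One pooled percentage per arm cannot separate the two sources, and the exposure table is not linked to the adverse event tables.

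**Working it through.** **Inputs from the documents.** CR 87% versus 70% (Protocol 9.2); consolidation cycles of 28 to 35 days, up to three (Table 5); a 30-day tail (9.4.4); marrow assessment by Day 42 of each of the first two cycles (4.1, 8.5.1).

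**Assumptions.** The first two cycles last 56 to 84 days together; all responders take the same number of consolidation cycles; the responder proportions equal the CR rates (questioned under the objection).

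**The plan's own figure.** The documents give no figure for adverse event exposure. The CR rates do feed a stated power, which reproduces: 0.70 versus 0.42, 90 per arm, two-sided 0.05, pooled z. z = (0.28 − 1.96 × 0.0740) / 0.0710 = 1.90, so power is 97.1%, against the stated > 97%.

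**Step 1: mean TEAE window.** Window = two-cycle length + 30 + (responder proportion × cycles × cycle length), in days.

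| First two cycles | Consolidation | ENTO | Placebo | Difference | Ratio |
|---|---|---|---|---|---|
| 84 | 3 × 35 | 205.3 | 187.5 | 17.8 | 1.095 |
| 84 | 3 × 28 | 187.1 | 172.8 | 14.3 | 1.083 |
| 56 | 3 × 35 | 177.3 | 159.5 | 17.8 | 1.112 |
| 84 | 1 × 28 | 138.4 | 133.6 | 4.8 | 1.036 |
| 56 | 1 × 35 | 116.5 | 110.5 | 6.0 | 1.054 |

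**Step 2: an event with the same constant daily hazard h in both arms.** Let S be the short window (two cycles + 30 days), L the long one (S + consolidation) and r the responder proportion. Crude risk = (1 − r)(1 − e^(−hS)) + r(1 − e^(−hL)). The difference between arms is therefore 0.17 × (e^(−hS) − e^(−hL)).

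Example with S = 114 and L = 219: a placebo percentage of 30% requires h = 0.001926 per day. Then e^(−hS) = 0.803 and e^(−hL) = 0.656, so the difference is 0.17 × 0.147 = 2.5 points. ENTO shows 32.5% with a true rate ratio of 1.

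Over two-cycle lengths of 56 to 84 days and three cycles of 28 to 35 days, the formula gives these excesses on ENTO:
- placebo 10%: 0.8 to 1.1 points
- placebo 30%: 2.2 to 3.0 points
- placebo 50%: 3.1 to 4.4 points
- largest at any placebo percentage: 3.4 to 4.9 points

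With one consolidation cycle the largest excess is 1.4 to 2.1 points.

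**Step 3: an event arising only in consolidation, with risk q among those treated.** Excess = (0.87 − 0.70) × q = 0.17q: 6.8 points at q = 40% (34.8% versus 28.0%), 8.5 at 50%, 13.6 at 80%. If the same term can also occur earlier, subjects already counted add nothing. With an independent 40% risk before consolidation, the 6.8 points become 0.17 × 0.40 × 0.60 = 4.1.

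**Step 4: sensitivity to the responder gap.** At 87% versus 80% with three cycles, the largest constant-hazard excess is about 2 points. At 87% versus 86% the windows differ by about one day and the excess is near zero.

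**Step 5: does person-time repair it?** Under constant hazard, events per person-time return a ratio of 1.00. If all events fall in the first two cycles, equal counts are divided by a longer ENTO time, and the ratio becomes 1/1.112 = 0.90 to 1/1.083 = 0.92, which makes ENTO look safer than it is.

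**The case against.** The strongest reply is that 17 points is not the gap that decides who continues. Continuation depends on CR, CRh or CRi. The 87% comes from 13 of 15 subjects with CR or CRi (Protocol 2.2). The 70% is CR alone, based on 68% in patients aged 60 or over, while the trial enrols from age 18. Elsewhere the protocol cites CR rates of 86 to 88% on standard care in favourable-risk *NPM1* disease, and a composite rate of 76% on ENTO in 25 patients (2.4). The real gap could be small or absent. This stands, and it is why the size must be given as a range that reaches zero.

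It also stands that three cycles for every responder is a ceiling, and that transplant ends study medication, so more responders could mean more transplants and shorter exposure. For a typical event the artefact is well inside sampling error: at 30% versus 32.5% with 90 per arm, the standard error is √(0.30 × 0.70/90 + 0.325 × 0.675/90) = 6.9 points. Whole-regimen percentages are a legitimate measure of overall burden, since consolidation belongs to the treatment of interest in 9.4.2.1.

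Two replies go less far. The exposure table in SAP 6.3 shows a difference in treatment length but does not say which adverse events it explains. Protocol 9.4 leaves detail to the SAP, and the only SAP was written after termination for an abbreviated report, so its silence does not show what a full SAP would have held. The gap in the protocol's description remains.

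**Conclusion.** The point holds as a conditional weakness of the planned 180-subject safety comparison. If ENTO raises the proportion in CR, CRh or CRi as the plan assumes for CR, the pooled percentages would carry an excess not caused by the drug. At a 17-point gap and three cycles it is about 1 to 5 points for constant-hazard events and 0.17 times the risk for consolidation-only events. These figures rest on the constant hazard, cycle lengths and uniform uptake stated above.

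A reader might infer that ENTO is bound to look more toxic. The documents do not support that: the CR/CRh/CRi rate on placebo is not given, and transplant or early stopping of ENTO could reverse the direction. A reader might also take 34.8% versus 28.0% as the expected size. That needs the full 17-point gap, every responder treated, and no earlier occurrence of the same term. Nor does it follow that the crude percentages are wrong and should go.

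The SAP plans no inference and reports 15 randomised subjects, so the effect on the abbreviated report is small.

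**What to change.** In Protocol 9.4.4, and in SAP 6.5.1 where numbers allow:

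1. Keep the overall TEAE percentages as the summary of total burden.
2. Add a by-arm table of TEAEs from C1D1 to the post-Chemotherapy Cycle 2 assessment in all treated subjects. Name it as the between-arm comparison least affected by differential treatment length, since it precedes the response gate.
3. As descriptive support only, add TEAEs in later consolidation among subjects who enter it, and exposure-adjusted rates for SAEs and common preferred terms.

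The cost is programming for two or three tables from adverse event and dosing dates already collected, and a longer safety section. The limits should be stated beside the tables. The consolidation table conditions on response after randomisation. Person-time rates can favour ENTO if events cluster early. The early table is not fully neutral either, because the Chemotherapy Cycle 2 regimen depends on the response to Induction Cycle 1. With 15 subjects, rates by preferred term would say little, so for the abbreviated report a sentence noting the limitation may be enough.

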9.5 Timing of Analyses

9.5.1 Data Monitoring Committee

An independent DMC, consisting of two expert hematologists and one expert biostatistician will monitor emerging safety and efficacy data from this trial on an ongoing basis. The DMC will provide a suitable recommendation to the Sponsor for appropriate study direction. Such direction may include continuation of the trial as planned, modification of study conduct/design or early termination based on safety or futility. A DMC charter delineates the responsibilities of the DMC and its interactions with other trial components. Data monitoring committee analyses will be focused on safety and efficacy endpoints and will be conducted regularly as outlined in the DMC charter.

9.5.2 Blinded Review of EFS Events

Prior to unblinding for the primary endpoint analysis, the sponsor will review the number of EFS events achieved. If the rate of events is slower than anticipated, the sponsor may propose an increase in sample size in order to achieve the events necessary for the confirmatory analysis of EFS. The increase will be based on the original sample size assumptions for hazard ratio and two-year EFS rate of the placebo group. The proposed sample size increase will be shared with the DMC and appropriate regulatory agency prior to implementation. Given that the review will be conducted in a blinded fashion, no adjustment for Type 1 error is proposed.

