2.4 Benefit/Risk Assessment

NPM1-mutated AML constitutes a genetically defined subset of AML comprising approximately 30% of newly diagnosed subjects and is recognized as a distinct disease entity in the 2017 WHO classification of myeloid neoplasms and acute leukemia ([Patel 2012, Arber 2016](#)). *NPM1* mutation is commonly associated with normal cytogenetics in subjects < 60 years of age. In the absence of concurrent *FLT-3* internal tandem duplication (ITD) (or presence at low allelic ratio), or other adverse cytogenetic abnormalities, subjects with *NPM1* mutation are thought to be in the favorable risk category ([Table 1](#)) with CR rates of 86 to 88% with current standards of care ([Angenendt 2019](#)). Concurrent *FLT-3* ITD at high allelic ratio confers ELN intermediate risk status ([Patel 2012, Dohner 2017](#)). *NPM1*-mutated AML patients with additional adverse cytogenetic features are usually older than 60 years of age and/or have a history of myelodysplastic syndrome, and poorer prognosis with CR rates of 66.3% and a 5-year OS of 19.5% ([Angenendt 2019](#)).

As of 31 January 2021, 20 clinical studies of ENTO have been conducted in which approximately 1259 subjects received ENTO either alone or in combination with other agents. Detailed descriptions of ENTO clinical studies conducted to date including results, where available, may be found in the Investigator's Brochure ([Section 4.0, Clinical Studies](#)).

In the GS-US-339-1559 study, ENTO alone or in combination with 7 + 3 chemotherapy was generally well-tolerated. Most treatment-emergent adverse events (TEAEs) were consistent with those expected following treatment with intensive induction and consolidation chemotherapy as well as from complications of underlying AML. Commonly reported TEAEs/laboratory abnormalities are listed in [Table 2](#).

CONFIDENTIAL

Protocol KB-ENTO-3001 v4.0 Global
(Amendment 3.0 Global)**Table 2: Common Treatment-emergent Adverse Events Reported in Study GS-US-339-1559 Regardless of Causality**

TEAEs	Total n (%)	Grade 3 or 4 n (%)
Any TEAE	53 (100)	53 (100)
Nonhematologic AEs/laboratory abnormalities reported in > 25% of subjects		
Nausea	37 (70)	1 (2)
Diarrhoea	35 (66)	5 (9)
Oedema peripheral	31 (59)	0
Alanine aminotransferase increased	30 (57)	3 (6)
Blood bilirubin increased	26 (49)	6 (11)
Rash (maculopapular)	23 (43)	7 (13)
Decreased appetite	22 (42)	2 (4)
Constipation	21 (40)	0
Headache	21 (40)	0
Dyspnoea	20 (38)	2 (4)

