9.4.3 Secondary Endpoint(s)

The secondary endpoint variables and their population level summary measures will be described in each of the following sections. The evaluation of the population for the trial, treatments of interest, and the possible intercurrent events are as described in [Section 9.4.2.1](#). All secondary endpoints will include death as part of definition of the variable. Intercurrent events of additional leukemic therapy and premature study treatment discontinuation will be ignored for the primary evaluation of these endpoints. Additional information on the handling of missing data and sensitivity analyses will be detailed in the SAP.

CONFIDENTIAL

Protocol KB-ENTO-3001 v4.0

(Amendment 3.0)

Event-free survival

Event-free survival (EFS) is defined as time from randomization to the earliest of induction treatment failure (ITF), relapse for those who achieve CR, or death from any cause. ITF is failure to achieve morphological CR after completion of the last cycle of induction chemotherapy (no later than Day 42 of the last cycle of induction). Subjects who experience ITF will be treated as events at Day 1.

Subjects who do not experience an event (ITF, relapse from CR, or death) will be censored at their last study evaluation at which they were relapse free. Event-free survival will be estimated using the method of Kaplan-Meier (K-M) and summarized by treatment group. Differences between the treatment groups will be assessed with the log rank test stratified by age (<60 vs \geq 60 years) and choice of anthracycline in induction (daunorubicin vs idarubicin). The population level summary measure will be the adjusted hazard ratio as calculated from a Cox proportional hazards model with effects for treatment, age, and choice of anthracycline in induction.

Relapse free survival

For subjects who achieve CR, relapse free survival (RFS) is defined as the time from CR to morphologic relapse as assessed by the study site investigator or death from any cause, whichever comes first. Subjects who do not experience a relapse or death will be censored at the last study evaluation at which they were relapse free. RFS will be estimated using the K-M method and summarized by treatment group. The population level summary measure will be the adjusted hazard ratio as calculated from a Cox proportional hazards model with effects for treatment, age, and choice of anthracycline in induction.

Overall survival

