9.5.4 EFS Analysis

A final EFS analysis will be conducted once the pre-specified number of events have been reported and the resulting database is cleaned and locked.

CONFIDENTIAL

Protocol KB-ENTO-3001 v4.0

(Amendment 3.0)

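### The blinded EFS review sizes any increase from the original placebo EFS rate, so if events are slow because the event hazard is lower, the increase is too small; the main cost is delay

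*Protocol*

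**What the plan says.** Protocol 9.5.2 places a blinded count of EFS events before unblinding for the primary analysis. The trigger is: "If the rate of events is slower than anticipated, the sponsor may propose an increase in sample size". The stated purpose is to reach the events needed for the confirmatory EFS analysis. The basis of the calculation is: "The increase will be based on the original sample size assumptions for hazard ratio and two-year EFS rate of the placebo group". Any proposal goes to the DMC and the regulator before it is implemented. No numerical trigger is given.

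Protocol 9.2 sets the original inputs: control two-year EFS 63% (hazard 0.231), hazard ratio 0.6, and "a total of 124 events (70 in the placebo arm, 54 in the ENTO arm) would be sufficient to provide 80% power", "assuming 2-sided alpha = 0.05 and a total study duration of 60 months". Protocol 9.5.4 makes the analysis event-driven: "A final EFS analysis will be conducted once the pre-specified number of events have been reported". Protocol 4.3 ends the study no later than five years after the last subject enrolls. SAP 4.2 repeats the 124-event target. The SAP does not describe the blinded review, and neither document brings the observed pooled event rate into the calculation.

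**The concern.** The review exists to correct for slow events. Two different inputs are involved. The number of events depends on the hazard ratio, alpha and power, and keeping HR 0.6 in a blinded review is sound. The number of subjects needed to produce those events by a given date depends on the event rate. If events are slow because fewer subjects per year fail, relapse or die, then 63% is too low a two-year EFS rate, and sizing on it understates the subjects required.

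A higher rate is possible. Protocol 9.2 says "a conservative estimate of 70% CR rate for placebo is assumed for sample size determination", while Protocol 2.4 describes favorable-risk *NPM1*-mutated disease "with CR rates of 86 to 88% with current standards of care". Induction failure is itself an EFS event, so two-year EFS cannot much exceed the CR rate. True rates of 70% or 75% therefore both imply CR above the assumed 70%, and 75% is best read as an upper illustration.

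At stake is the date of the EFS analysis. EFS is tested first in the secondary hierarchy (Protocol 9.4.3), so a late EFS result also holds back RFS and OS.

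**Working it through.** **Inputs.** From Protocol 9.2: two-year EFS 63%, HR 0.6, 124 events, two-sided alpha 0.05, 80% power, 60 months, 180 subjects. From Protocol 4.1: 1:1 allocation. From Protocol 4.3: the five-year limit. Assumed, because not in the documents: exponential EFS, no losses, uniform accrual over A = 0, 1, 2 or 3 years, and true two-year EFS of 70% or 75%.

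**The plan's own figures.** Hazard = -ln(0.63)/2 = 0.231, as stated. Events by Schoenfeld: 4(1.960 + 0.842)²/(ln 0.6)² = 120.3, so 121. By Freedman: (1.6/0.4)² × (1.960 + 0.842)² = 125.6, so 126. The plan's 124 lies between them. No event rate enters either formula.

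**Subjects needed by T = 5 years.** Event probability in an arm with hazard h: p(h) = 1 - [exp(-h(T-A)) - exp(-hT)]/(hA), or 1 - exp(-hT) when A = 0. With q the mean of p(h) and p(0.6h), N = 124/q. The hazards are 0.231 (63%), 0.178 (70%) and 0.144 (75%).

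- A = 0: q = 0.5925, 0.5022, 0.4317, so N = 210, 247, 288.
- A = 3: q = 0.4627, 0.3837, 0.3247, so N = 268, 324, 382.

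| Accrual (years) | N sized on 63% | N needed at 70% (short by) | N needed at 75% (short by) | Month of 124th event, 70% / 75% |
|---|---|---|---|---|
| 0 | 210 | 247 (37) | 288 (78) | 77.3 / 95.8 |
| 1 | 224 | 266 (42) | 311 (87) | 75.7 / 92.4 |
| 2 | 243 | 291 (48) | 342 (99) | 73.7 / 88.4 |
| 3 | 268 | 324 (56) | 382 (114) | 72.0 / 84.6 |

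The last column uses the N sized on 63%. Against 60 months, the delay is about 12-17 months at 70% and 25-36 at 75%.

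**Does the Protocol 4.3 limit come first?** The limit is at A + 5 years. Power = Φ(|ln 0.6|√D/2 - 1.96), which is 81.2% at D = 124.

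| Accrual (years) | Limit (months) | Events by limit at 70% (power) | Events by limit at 75% (power) |
|---|---|---|---|
| 0 | 60 | 105.5 (74.6%) | 90.7 (68.1%) |
| 1 | 72 | 119.7 (79.8%) | 103.5 (73.8%) |
| 2 | 84 | 124 reached first | 119.1 (79.6%) |
| 3 | 96 | 124 reached first | 124 reached first |

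The row for A = 0 is a mathematical boundary, since all subjects would enroll on one day.

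**If the rule instead fills the event shortfall at the original rate.** Take 180 subjects over 3 years and count events to year 8, the Protocol 4.3 limit for those subjects. Then q = 0.682 (63%), 0.591 (70%), 0.516 (75%). At 70%, 180 × 0.591 = 106.3 events; the shortfall is 17.7, and 17.7/0.682 gives 26 added subjects. At 75%, 92.9 events; 31.1/0.682 gives 46 added. The review precedes the primary analysis, which follows 180 subjects completing Cycle 2, so added subjects enroll after it. Assume they enroll from year 3.2 at 60 per year; the five-year clock then restarts from the last of them.

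- 70%: limit 3.2 + 26/60 + 5 = 8.63 years; 125.8 events by then, power 81.7%; 124th event at about 8.5 years.
- 75%: limit 3.2 + 46/60 + 5 = 8.97 years; 122.6 events by then, power 80.7%; 124th event at about 9.1 years.

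Under the original assumptions, 180 subjects reach 124 events at about 8.1 years, so the delay is roughly 4 and 12 months.

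**The case against.** Several points on the other side stand. The analysis waits for its events, so power is normally protected. The increase is optional, and the DMC and regulator see it first, so a poor projection could be caught, although 9.5.2 does not let them change its basis. A slow pooled count does not disprove 63%. Slow accrual produces it with the original rate intact, and so does a larger effect. For 180 subjects to year 8 with 3-year accrual, placebo 63% with HR 0.35 gives 69.5 + 36.7 = 106.2 events with power above 99%, matching the 106.3 from placebo 70% with HR 0.6. The review would also rest on few events: about 46 expected at year 3.2 under 63%, and 37 under 70%. Keeping prespecified inputs is therefore a defensible choice, not an oversight in every case.

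A reader might go further and infer that feeding the original inputs back in returns about the planned 180, so that the clause yields no real increase and costs substantial power. That needs a sizing horizon near 8 years, which neither document states for EFS. The printed 70/54 split is slightly closer to such a horizon (about 70/54) than to 60 months (about 72/52 to 73/51), but two or three events cannot establish a horizon when accrual and losses are not given. At the stated 60 months, 180 subjects give only 83-107 events even if 63% is true, so the original inputs do call for more subjects. A reading with no increase would also defeat the purpose stated in 9.5.2.

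A reader might also cite "Subjects who experience ITF will be treated as events at Day 1" against the exponential model. If two-year EFS stays at 63%, those failures move events earlier and the count at the review is not slow, so the clause would not be triggered. That is a question about 9.2, not support for this point.

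**Conclusion.** The point holds conditionally. When slow events are due to a lower hazard, the rule in 9.5.2 undersizes the increase. Sized at 60 months, it is short by about 37-56 subjects at a true two-year placebo EFS of 70% and 78-114 at 75%, which delays the 124th event by about 12-17 and 25-36 months. Power falls below 80% only where the Protocol 4.3 limit comes first: not with 3-year accrual; about 79-80% with 2-year accrual and 75%; about 74% with 1-year accrual and 75%. If the rule is read as filling the shortfall, power stays at about 80% or more and the delay is months. The direction does not depend on the model; the sizes rest on exponential EFS, no losses and assumed accrual.

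The documents do not support a claim that the clause gives no increase, or that a large power loss is to be expected. EFS is secondary. SAP 4.1 and 4.2 record that the trial stopped at 15 randomized subjects with no formal testing, so no result is affected. Severity is low.

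**What to change.** In Protocol 9.5.2, replace the basis of the increase with: *the original hazard ratio, the observed blinded pooled EFS event rate and actual accrual*. Keep HR 0.6 and 124 events; with HR and 1:1 allocation fixed, the pooled rate determines both arm rates. State the study duration used in the projection, because Protocol 9.2 gives 60 months in total and Protocol 4.3 allows five years after the last subject.

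The cost is one clause and one stated duration. The review stays blinded, so the protocol's reason for no Type 1 error adjustment is unchanged. The small downside is that, if the true effect is larger than HR 0.6, the pooled rate may call for more subjects than needed.
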